Participation in this study is not intended to change the routine treatment received as determined by their attending physicians. Patients will be treated according to the routine medical practice in terms of visit frequency and types of assessments performed.

Upon site initiation, investigators will consecutively enroll eligible patients into this study after obtaining patients' informed consent. The observation period for each patient is planned to be 60 months, starting from the patients who received lorlatinib enrolled in this study and ending at the earliest occurrence of the completion of 60 months of follow-up, death, loss to follow-up, or withdrawal from the study. The study data will be generated from the attending physician's routine clinical assessment during standard care. The data source used for data collection will be from electronic medical records/medical records or medical charts or other approved data source.

The study duration will be approximately 6 years. The enrollment period is planned to be about 12 months (from first site initiation, until the planned number of patients reached). The follow-up period per patient is up to 60 months from the time patients who received lorlatinib enrolled in this study. The interim analysis will be performed when half TTD events happen. The study is expected to be closed in about Oct 2030.

Safety and effectiveness assessments were performed throughout the treatment period and at the end-of-study visit. Routine safety assessments included the collection and evaluation of AEs, concomitant medications, vital signs, and body weight. Particular attention was given to AEs consistent with the lorlatinib toxicity profile (including lipid elevation, cognitive and mood disorder, etc.). Additional safety assessments performed at selected visits included ECOG PS, clinical laboratory tests, ECGs, and LVEF imaging. Contrast-enhanced computed tomography (CT) or magnetic resonance imaging (MRI) was used for tumor assessment at screening, at baseline, 4 weeks after lorlatinib treatment and then every 8-12 weeks. For patients with brain metastases,

RANO-BM criteria was used for intracranial lesions. Gadolinium-enhanced brain MRI is recommended at baseline and 4 weeks after lorlatinib treatment.

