7.2 Efficacy Assessments

7.2.1 Tumor Response Assessment

Objective tumor response will be measured using RECIST v1.1 (see Appendix 3) and assessed by the investigator (INV) in real world clinical practice .

Imaging tumor assessments at screening are to be performed within 28 days prior to commencing study treatment. All measurements should be recorded in metric notation using a ruler or calipers.

Investigators are encouraged to select greater than one lesion, representative and reproducible and to include the largest lesion, when identifying target lesions to be followed.

Post-baseline tumor assessments will be performed at the end of the first 8 weeks

then every cycle (within 7 days of the start of subsequent cycle including Day 1 of subsequent cycle), using the same method and technique used to characterize lesions identified at baseline. Imaging serves also as safety assessment to monitor/exclude pulmonary toxicity.

Subjects with no evidence of disease progression at the time of treatment discontinuation, should be followed up until disease progression, regardless of the start of any new cancer therapy. Repeat tumor assessments are suggested approximately every 4 weeks from the date of CT/MRI at the end of study treatment in the appropriate setting.

All subjects should be followed up for subsequent cancer therapies and survival status regardless of the reasons for discontinuation from study drug treatment. Telephone contact or other means to obtain timely regular follow-up is recommended. The information for subsequent therapies collected and recorded on the CRF should include enumeration of subsequent treatment, including drugs administered, date of initiation

and discontinuation of each drug. This may be conducted by telephone for unresponsive subjects. As per RECIST v1.1 guidelines, PR and CR do not need to be confirmed following initial response documentation. However, subjects with documented PR or CR should still be followed with regular assessments for the duration of the study to see if there is a change in status with time.

The same method and technique should be used to characterize each lesion identified and reported at Baseline, during the study treatment period, and during follow up.

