9.2.4 Definitions of Secondary Efficacy Endpoints

Real world Intracranial Objective Response Rate is defined as the proportion of subjects with a BOR of either CR or PR of intracranial disease, where BOR is the best response recorded from the start of treatment until disease progression or start of other anticancer therapy in real world setting. As per RECIST v1.1 guidelines, PR and CR do not need to be confirmed following initial response documentation.

Real world Objective Response Rate is defined as the proportion of subjects with a BOR of either CR or PR, where BOR is the best response recorded from the start of treatment until disease progression or start of other anticancer therapy in real world setting. As per RECIST v1.1 guidelines, PR and CR do not need to be confirmed following initial response documentation.

Real world Disease control rate is defined as the proportion of patients with complete response (CR) or partial response (PR) or subjects with stable disease (SD) as per investigator assessment according to RECIST 1.1 criteria in real world setting.

Overall Survival is defined as the time from start of treatment to the date of death for any cause. In the absence of confirmation of death, survival time will be censored at the last date the subject is known to be alive.

Real world Intracranial Time To Progression is defined as the time from randomization to the date of the first documentation of objective progression of intracranial disease, based on either new brain metastases or progression of existing brain metastases in real world setting.

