9.2.5 Analysis of Secondary Endpoints

rwPFS, IC-TTP and Overall Survival will be summarized using Kaplan-Meier methods and displayed graphically. The 1/2/3/4/5-year rwPFS, IC-TTP and survival probability will be estimated using Kaplan-Meier methods and the 2-sided 95% CI will be provided. Potential influences of other demographic, baseline characteristics including biomarker profile use parametrical test, χ^2 or Fisher exact test. Objective Response Rate will be summarized for the SAT Population based on the investigator's assessment. The number and percent of subjects achieving objective response (CR or PR) will be summarized along with corresponding 2-sided 95% CI using the binomial distribution.

Intracranial Objective Response Rate will be summarized for the SAT Population based on the investigator's assessment. The assessment of intracranial response will be conducted on subjects with measurable and unmeasurable CNS metastases. The number and percent of subjects achieving objective response (CR or PR) will be summarized along with corresponding 2-sided 95% CI using the binomial distribution.

Subgroup analysis is considered to be conducted by baseline characteristics such as CNS (Yes/No), TP53 status (Yes/No), ALK-EML4 fusion variant (V1, V2, V3) in patients with baseline who receive lorlatinib in first line. Depending on the actual sample size at the time of analysis, adjustment by either combining or re-classifying the subgroups will be applied as needed.

Subgroup comparisons, where is applicable, will be performed using the Kaplan-Meier method and the log-rank test. Statistically significant level of $\alpha=0.05$ (two sides) is used for tests.

The qualitative exploratory endpoints will be categorized and summarized descriptively by count and percentage of patients. Missing data will be categorized by missing, unknown, or can't be determined.

The interim analysis will be performed when the completion of 2.5 year follow-up in late patient. The final full analysis will take place at the time of data cut-off (i.e. the completion of 60-month follow-up for all the participants).

Descriptive statistics will be used to summarize subject characteristics, study conduct, subject disposition, treatment administration/compliance, and safety parameters. Data will also be displayed graphically, where appropriate.

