APPENDIX 3 RECIST Version 1.1

Adapted from E.A. Eisenhauer, et al: New response evaluation criteria in solid tumors: Revised RECIST guideline (version 1.1). European Journal of Cancer 45 (2009) 228–247.

CATEGORIZING LESIONS AT BASELINE

Measurable Lesions

Lesions that can be accurately measured in at least one dimension.

Lesions with longest diameter twice the slice thickness and at least 10 mm or greater when assessed by CT or MRI (slice thickness 5-8 mm)

Lesions with longest diameter at least 20 mm when assessed by Chest X-ray

Superficial lesions with longest diameter 10 mm or greater when assessed by caliper

Malignant lymph nodes with the short axis 15 mm or greater when assessed by CT.

NOTE: The shortest axis is used as the diameter for malignant lymph nodes, longest axis for all other measurable lesions.

Non-measurable disease

Non-measurable disease includes lesions too small to be considered measurable (including nodes with short axis between 10 and 14.9 mm) and truly non-measurable disease such as pleural or pericardial effusions, ascites, inflammatory breast disease, leptomeningeal disease, lymphangitic involvement of skin or lung, clinical lesions that cannot be accurately measured with calipers, abdominal masses identified by physical exam that are not measurable by reproducible imaging techniques.

Bone disease: Bone disease is non-measurable with the exception of soft tissue components that can be evaluated by CT or MRI and meet the definition of measurability at baseline.

Previous local treatment: A previously irradiated lesion (or lesion subjected to other local treatment) is non-measurable unless it has progressed since completion of treatment.

Normal sites

Cystic lesions: Simple cysts should not be considered as malignant lesions and should not be recorded either as target or non-target disease. Cystic lesions thought to represent cystic metastases can be measurable lesions, if they meet the specific definition above. If non-cystic lesions are also present, these are preferred as target lesions.

Normal nodes: Nodes with short axis <10 mm are considered normal and should not be recorded or followed either as measurable or non-measurable disease.

RECORDING TUMOR ASSESSMENTS

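### Intracranial ORR is tied to RANO-BM in section 3.1 but to a RECIST v1.1 rule in its own definition, and intracranial TTP names no criterion where it is defined

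*Protocol*

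**What the plan says.** Section 3.1, in describing tumour imaging, says of patients with brain metastases that "RANO-BM criteria was used for intracranial lesions". RANO-BM is not mentioned again.

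Section 7.2.1 gives the general rule: "Objective tumor response will be measured using RECIST v1.1 (see Appendix 3) and assessed by the investigator (INV) in real world clinical practice". It makes no exception for lesions in the brain.

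Section 9.2.4 defines the two intracranial endpoints:

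- For IC-ORR: "Real world Intracranial Objective Response Rate is defined as the proportion of subjects with a BOR of either CR or PR of intracranial disease". The same paragraph closes with "As per RECIST v1.1 guidelines, PR and CR do not need to be confirmed following initial response documentation".
- For IC-TTP, the event is "the first documentation of objective progression of intracranial disease, based on either new brain metastases or progression of existing brain metastases". No response criterion is named.

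Section 9.2.5 bases IC-ORR on the investigator's assessment and adds: "The assessment of intracranial response will be conducted on subjects with measurable and unmeasurable CNS metastases". It names no criterion either.

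The only response rules supplied are those under "APPENDIX 3 RECIST Version 1.1".

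**The concern.** IC-ORR and IC-TTP are both listed as secondary endpoints in section 2.2, and both depend on how an investigator classifies brain lesions. The protocol points that investigator to RANO-BM in one section and to RECIST v1.1 in others. Someone working from 3.1 would apply RANO-BM. Someone working from 7.2.1, Appendix 3 and the IC-ORR definition would apply RECIST v1.1.

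The choice determines what is written down at the time of the scan. Assessment is by the investigator at about 8 sites (section 3.1; the Introduction says about 6), and the protocol describes no central reading. If sites chose differently, the reported IC-ORR would mix readings made under two sets of rules, and the data would not show which rule produced which reading.

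**Working it through.** The protocol states no figure on this point, so the check is a comparison of the text, one endpoint at a time.

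**IC-ORR**

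1. Section 3.1 is specific to intracranial lesions and names RANO-BM.
2. Section 7.2.1 is general and names RECIST v1.1. Taken with 3.1 alone, the two can be reconciled as a general rule beside a specific one: RECIST for overall response, RANO-BM for the brain.
3. That reconciliation does not survive the IC-ORR paragraph in 9.2.4. There RECIST v1.1 is cited inside the definition of the intracranial endpoint, as the authority for accepting an unconfirmed intracranial CR or PR.
4. Two readings remain. Either RECIST v1.1 is the criterion for IC-ORR, which contradicts 3.1. Or RANO-BM is the measurement method and RECIST supplies only the confirmation rule, which is a hybrid that the protocol nowhere declares.

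**IC-TTP**

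1. Section 9.2.4 describes the event but names neither RECIST nor RANO-BM.
2. The only criterion stated for intracranial lesions is therefore RANO-BM, in 3.1.
3. No RANO-BM rules are given, so the protocol does not say what counts as progression of an existing brain lesion. The defect here is a criterion missing from the definition. It is not a conflict between two stated criteria.

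**Do the appended rules settle intracranial response?**

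1. Appendix 3 selects target lesions across the whole body, up to 2 per organ and 5 in all. It has no rule for a separate intracranial lesion set or an intracranial best response.
2. Section 9.2.5 includes patients whose CNS metastases are unmeasurable. In Appendix 3, the status table for patients with non-target disease only allows CR but has no PR category. That table is meant for protocols that enrol such patients, whereas section 4.1 requires at least one measurable lesion. Whether it applies to a patient whose brain disease alone is unmeasurable is not said.
3. So falling back on Appendix 3 still leaves intracranial response incompletely defined.

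**Size**

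The protocol does not reproduce the RANO-BM rules, so the number of patients who would be classified differently under the two criteria cannot be derived, and no shift in IC-ORR or IC-TTP is claimed.

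**The case against.** The strongest defence is that a specific rule sits beside a general one. Section 7.2.1 never mentions the brain, and 3.1 does. RECIST enters the IC-ORR paragraph only through a sentence on confirmation, which is repeated word for word in the overall ORR paragraph and may simply have been copied. Where section 9.2.4 means to assign RECIST as the criterion, as for disease control rate, it says so directly, and the IC-ORR definition has no such clause. This stands as far as it goes: 7.2.1 alone is no contradiction of 3.1. It still leaves the undeclared hybrid, and copied text in a definition remains in force until it is changed.

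The setting also limits the harm. Section 9.1 calls the study descriptive, IC-ORR is one of many secondary endpoints, and the limitations text in section 10.2 already concedes that routine assessment may define response and progression inconsistently. That is fair on weight. But acknowledging variation in practice does not justify giving sites two criteria. A statistical analysis plan could fix the derivation, but it could not recreate readings made under another rule.

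A reader might infer three stronger points that the protocol does not support:

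- *IC-TTP also has two conflicting criteria.* RECIST reaches IC-TTP only by inference from 7.2.1 and Appendix 3. Its definition does not cite it.
- *The effect can be put in percentage points.* Applying the 37 of 149 lorlatinib patients with baseline brain metastases in the earlier randomised trial (Introduction) to about 100 patients gives roughly 25, and 1/25 is 4 points per patient. At an assumed 20 to 40 patients it is 1/20 = 5.0 down to 1/40 = 2.5 points. This is the arithmetic of any proportion. It does not say how many patients would be reclassified, and the 25% share is borrowed from another trial.
- *The conflict spoils comparison with the intracranial response figures in the Introduction.* The protocol does not say which criterion produced those figures. They cover measurable brain metastases only, so the comparison is already limited by population.

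**Conclusion.** The concern holds for IC-ORR: as written, the endpoint has either two conflicting criteria or an undeclared hybrid, and investigator readings across sites could mix them. For IC-TTP the finding is narrower: the definition names no criterion, and the only one stated for intracranial lesions comes without rules.

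The size of the effect cannot be derived from the protocol. Two secondary endpoints are touched. TTD, defined in section 9.2.2 by discontinuation of lorlatinib, is not directly affected. The conclusion rests on the protocol text alone and assumes that no separate site instruction already fixes the intracranial criterion. It is worth correcting because the contradiction is explicit, the remedy is cheap, and readings already made under the wrong rule may not be recoverable.

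**What to change.** 1. Choose one criterion for intracranial response and progression, and name it for both IC-ORR and IC-TTP in sections 3.1, 7.2.1, 9.2.4 and 9.2.5.
2. State the confirmation rule that applies under that criterion. If RANO-BM is kept, replace the RECIST sentence in the IC-ORR paragraph. Deleting it without a replacement would leave IC-ORR with no confirmation rule in its definition.
3. If RANO-BM is kept, append its rules. Under either criterion, say how unmeasurable CNS disease is classified, since 9.2.5 includes it.
4. State that RECIST v1.1 governs overall response, so that 7.2.1 and the intracranial rule no longer overlap.

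The cost is protocol wording and site instruction. The protocol does not show whether RANO-BM calls for any further data item to be recorded, so this should be checked when its rules are appended. The change is best made before more intracranial readings accumulate.

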3.2 Safety Plan

The overall safety profile and toleration of lorlatinib and locally therapy will be based on AEs and laboratory abnormalities with regard to frequency, severity (in accordance with CTCAE v5.0), timing and relationship with study drug and treatment mode. Throughout the study, all patients treated with lorlatinib are followed for safety to assess the safety of lorlatinib, including AEs leading to dose modification, interruption or discontinuation of lorlatinib and other reasons for dose modification, interruption or discontinuation of lorlatinib in the medical records.

4. SUBJECT SELECTION

Subject eligibility should be reviewed and documented by an appropriately qualified member of the investigator's study team before patients are included in the study.

4.1 Inclusion Criteria

Subjects must meet all of the following inclusion criteria to be eligible for enrollment into the study:

1. Diagnosis:

- a. Study Population: Patients with histologically or cytologically confirmed diagnosis of locally advanced [(Stage IIIB/C not amenable for multimodality treatment) or metastatic (Stage IV) by American Joint Committee on Cancer (AJCC) v 7.0] ALK-positive NSCLC where ALK status is determined by the Ventana ALK (D5F3) Companion Diagnostic (CDx) IHC test performed on the Ventana ULTRA or XT Platforms, FISH, PCR, or next generation sequencing (NGS), or circulating tumor DNA (ctDNA).

- b. Tumor Requirements: At least 1 measurable target lesion per RECIST v. 1.1 that has not been previously irradiated. Brain metastases are allowed.
 2. No prior systemic treatment for advanced (Stage IIIB/C not amenable for multimodality treatment) or metastatic (Stage IV) disease.
 3. Eastern Cooperative Oncology Group Performance Status (ECOG PS) 0, 1, 2 or 3.
 4. Age ≥ 18 years.
 5. Adequate Liver Function, including:
 - a. Total serum bilirubin ≤ 1.5 x ULN;
 - b. Aspartate Aminotransferase (AST) and Alanine Aminotransferase (ALT) ≤ 2.5 x ULN (≤ 5.0 x ULN in case of liver metastases).
 6. Life expectancy at least 6 months.
 7. Serum pregnancy test (for females of childbearing potential) negative at screening. Female patients of non-childbearing potential must meet at least 1 of the following criteria:
 - a. Achieved postmenopausal status, defined as follows: cessation of regular menses for at least 12 consecutive months with no alternative pathological or physiological cause (which may be confirmed with a serum follicle-stimulating hormone [FSH] level confirming the postmenopausal state if appropriate);
 - b. Have undergone a documented hysterectomy and/or bilateral oophorectomy;
 - c. Have medically confirmed ovarian failure.
- All other female patients (including female patients with tubal ligations) are considered to be of childbearing potential.

8. Evidence of a personally signed and dated informed consent document indicating that the patient (or a legally acceptable representative) has been informed of all pertinent aspects of the study.

9. Willing and able to comply with scheduled visits, treatment plans, laboratory tests and other procedures.

4.2 Exclusion Criteria

Subjects presenting with any of the following characteristics/conditions will not be included in this clinical study:

1. Major surgery within 4 weeks prior to randomization. Minor surgical procedures (e.g., port insertion) are not excluded, but sufficient time should have passed for adequate wound healing.

2. Radiation therapy within 2 weeks prior to enrollment, including stereotactic or partial brain irradiation. Patients who complete whole brain irradiation within 4 weeks prior to randomization or palliative radiation therapy outside of the CNS within 48 hours prior to randomization will also not be included in the study.

3. Gastrointestinal abnormalities, including inability to take oral medication; requirement for intravenous alimentation; prior surgical procedures affecting absorption including total gastric resection or lap band; active inflammatory gastrointestinal disease, chronic diarrhea, symptomatic diverticular disease; treatment for active peptic ulcer disease in the past 6 months; malabsorption syndromes.

4. Known prior or suspected severe hypersensitivity to study drugs or any component in their formulations.

5. History of extensive, disseminated, bilateral or presence of Grade 3 or 4 interstitial fibrosis or interstitial lung disease including a history of pneumonitis, hypersensitivity pneumonitis, interstitial pneumonia, interstitial lung disease, obliterative bronchiolitis,

and pulmonary fibrosis.

6. Evidence of active malignancy (other than NSCLC, non-melanoma skin cancer, or localized prostate cancer or any in situ cancer which does not currently require treatment) within the last 3 years prior to randomization.

7. Concurrent use of any of the following food or drugs (consult the sponsor if in doubt whether a food or a drug fall into any of the above categories) within 12 days prior to the first dose of lorlatinib.

a. Known strong CYP3A inhibitors (e.g., strong CYP3A inhibitors: grapefruit juice or grapefruit/grapefruit related citrus fruits [eg, Seville oranges, pomelos], boceprevir, cobicistat, conivaptan, itraconazole, ketoconazole, posaconazole, ritonavir alone and with danoprevir or elvitegravir or indinavir or lopinavir or paritaprevir or ombitasvir or dasabuvir or saquinavir or tipranavir, telaprevir, troleandomycin, and voriconazole. The topical use of these medications (if applicable), such as 2% ketoconazole cream, is allowed.

b. Known CYP3A substrates with narrow therapeutic index, such as astemizole*, terfenadine*, cisapride*, pimozone, quinidine, tacrolimus, cyclosporine, sirolimus, alfentanil, fentanyl (including transdermal patch) or ergot alkaloids (ergotamine, dihydroergotamine) (*withdrawn from US market).

c. Known strong CYP3A inducers (e.g., carbamazepine, enzalutamide, mitotane, phenytoin, rifampin, St. John's Wort). d. Known P-gp substrates with a narrow therapeutic index (e.g., digoxin).

8. Other severe acute or chronic medical or psychiatric condition, including recent (within the past year) or active suicidal ideation or behavior, or laboratory abnormality that may increase the risk associated with study participation or investigational product administration or may interfere with the interpretation of study results and, in the judgment of the investigator, would make the patient inappropriate for entry into this study.

9. Participation in other studies involving investigational drug(s) within 2 weeks prior to study entry and/or during study participation.

